Prior to conducting the primary analyses, group differences in baseline measures will be evaluated to ensure that the group assignment was even. We will also inspect the

distributions of continuous variables (e.g., frequency condom use) for departures from normality. Variables that exhibit non-normal distributions will be subjected to normalizing transformations prior to analysis. If those transformations are unsuccessful, analysis will proceed using non-parametric tools. In addition, the rate of attrition between baseline and follow-up interviews will be evaluated to ensure that it is relatively constant across intervention conditions, and that there are no systematic differences in the variables of interest between participants who completed the study and those lost to follow-up. Missing data due to item non-response or loss to follow-up will be handled using the most appropriate method, depending on the amount of missing data, the assumptions of the missing data (completely at random, at random or non-ignorable) and the assumptions of the method of handling missing data. For example, for small amounts of missing data that are assumed to be missing at random, listwise or pairwise deletion (the default in most statistical packages) will be sufficient. Variables that differ significantly between those who returned for follow-up and those who did not can also be controlled for in regression analyses. Where appropriate, we will use statistical models that employ maximum likelihood techniques of parameter estimation, allowing us to use participants with incomplete data and avoid the potential bias caused by listwise deletion. These techniques are robust under conditions of missing at random so comparisons of groups will not be biased as long as missing data is ignorable. The number of planned comparisons will be limited based on a priori hypotheses, therefore the per comparison error rate of .05 will be used to evaluate significance of the specific aims. Exploratory or secondary analyses will be adjusted for multiple comparisons using the Bonferroni test.

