**Study Statistical Power.** Power analyses were done to assess the minimum detectable improvement needed for LARC uptake. A sample of 75 per group, using ITT approaches and assuming outcome if failure (dichotomous only) for patients who do not respond to follow-up surveys will provide 80% power to detect 23% difference between usual care and intervention patients on dichotomous outcomes, assuming an average success rate of 50% for maximum variability. For continuous outcomes, a follow-up sample size of 60 per group will provide 80% power to detect a .55 SD difference between usual care and intervention patients, or a medium linear effect over time (correlational structure CS with  $\rho=.5$ ).

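### Attrition covariates for the continuous scores are chosen by a significance screen that is not split by arm; a fixed set of baseline covariates would be safer and costs little

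*Combined protocol and SAP*

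**What the plan says.** Section IV.F (Data Analysis Plan, Phase II) plans two attrition checks. One is that the rate of loss is roughly equal across the arms. The other is that "there are no systematic differences in the variables of interest between participants who completed the study and those lost to follow-up". On adjustment it then says: "Variables that differ significantly between those who returned for follow-up and those who did not can also be controlled for in regression analyses".

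Around these sentences the plan leaves the missing-data method to later judgement, depending on the amount and assumed mechanism of loss. Listwise or pairwise deletion is accepted for small amounts assumed missing at random, with no threshold for small. Maximum likelihood is to be used where suitable. The analyses named are regression, change scores, analysis of variance and GEE.

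The Study Statistical Power paragraph gives the planned follow-up: "For continuous outcomes, a follow-up sample size of 60 per group will provide 80% power to detect a .55 SD difference". It counts non-responders as failures for dichotomous outcomes only. Section IV.E ranks retention as the leading scientific difficulty.

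The plan contains no completer-versus-lost comparison within arm, no fixed covariate list and no sensitivity analysis for non-ignorable loss.

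**The concern.** A non-significant difference between completers and those lost does not show that there is no difference, and the plan sets no margin or confidence bound. The more serious limit is the target of the screen. An arm contrast is biased when the women lost differ between arms, and a comparison made across both arms together can show nothing in that case. Comparing attrition rates by arm does not help, because the rates can be equal while different kinds of women leave each arm.

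At stake are the continuous scores: knowledge, self-efficacy, perceived benefit and motivation. If they are analysed on completers and the screen finds nothing, a biased contrast may be reported alongside a statement that no systematic differences were found.

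**Working it through.** **Inputs from the documents.** 75 per arm and 60 per arm followed (power paragraph), so 15 lost per arm, or 20%. Alpha .05 per comparison (IV.F); sidedness is not stated, so two-sided is assumed. Within-subject correlation .5 (power paragraph). Total N is inconsistent: 150 with 75 per arm under Aim 2 and in the power paragraph, but 160 in the Phase II paragraph of section IV, so both are carried.

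**Assumptions.** The size and direction of selective loss (0.5 to 1.0 SD) are not in the documents. No true intervention effect.

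**1. The plan's own figures.**
- Dichotomous: "will provide 80% power to detect 23% difference between usual care and intervention patients on dichotomous outcomes", at an average of 50%, means 38.5% versus 61.5%. Null SE = √(2×0.25/75) = 0.0816; alternative SE = √(2×0.385×0.615/75) = 0.0795. Power = Φ[(0.23 − 1.96×0.0816)/0.0795] = Φ(0.88) = 81%. Reproduced.
- Continuous: 0.55×√(60/2) = 3.01; Φ(3.01 − 1.96) = 85%, against 80% stated. This is conservative and does not affect the point.

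**2. Power of the completer-versus-lost screen.** Noncentrality = d×√(n₁n₂/(n₁+n₂)). For 120 versus 30 and d = 0.5: 0.5×√24 = 2.45; miss rate = 1 − Φ(2.45 − 1.96) = 31.2%. With the noncentral t:

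| Completers v lost | Basis | Miss rate at 0.5 SD |
|---|---|---|
| 120 v 30 | N=150, 20% lost | 31.8% |
| 128 v 32 | N=160, 20% lost | 29.0% |
| 120 v 40 | N=160, 60 per arm kept | 22.3% |
| 135 v 15 | N=150, 10% lost | 55.4% |
| 105 v 45 | N=150, 30% lost | 20.4% |
| 60 v 15 | within one arm | 59.9% |

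At 120 v 30, 80% power needs 0.58 SD. Running the screen within each arm would be weaker still.

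**3. Selection in opposite directions by arm, equal loss rates.** Losing 20% who differ from completers by d moves the completer mean by 0.2d from the randomised mean.
- Baseline contrast among completers at ±0.5 SD: 2×0.2×0.5 = 0.20 SD.
- Unadjusted follow-up contrast: 0.5×0.20 = **0.10 SD**.
- Change-score contrast: (0.5 − 1)×0.20 = **−0.10 SD**, so change scores reverse the bias without removing it.
- SE = √(2/60) = 0.183, and 0.10/0.183 = 0.55. Type I error ≈ Φ(0.55 − 1.96) + Φ(−0.55 − 1.96) ≈ 8.5%.

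Simulation (6,000 trials per row; 15 lost per arm; adjust for the baseline score only if the screen gives p<.05):

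| Shift by arm (SD) | Screen flags | Bias under the screen | Type I, screen | Type I, always adjusted |
|---|---|---|---|---|
| +0.5, −0.5 | 4.6% | 0.095 | 8.0% | 4.6% |
| +0.8, −0.8 | 4.0% | 0.152 | 13.8% | 4.7% |
| +1.0, −1.0 | 3.4% | 0.196 | 18.7% | 5.2% |
| +0.5, 0 | 23.0% | 0.039 | 5.6% | 5.0% |

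A separate simulation with a logistic dropout model at about ±0.5 SD gave a 5.1% flag rate. Bias was 0.11 SD without adjustment and 0.003 SD after adjusting for the baseline score.

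**4. A difference common to both arms.** The two completer means move together and the contrast is 0.2d − 0.2d = 0. Simulation at +0.5 in both arms gave bias 0.002 SD and type I error 4.8% with unadjusted completers.

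**5. Precision when loss is harmless.** Unadjusted SE = √(2/60) = 0.18. Adjusted for the baseline score: √((1 − 0.5²)×2/60) = 0.16.

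**The case against.** The strongest reply is that the plan does not rest on the screen. The adjustment sentence is permissive and additional, and maximum likelihood comes straight after it. Simulating the same dropout with every baseline value kept and an arm-by-time test gave bias 0.004 SD and type I error 4.7% (maximum likelihood) and 0.004 SD and 4.8% (exchangeable GEE) at ±0.5 SD. At ±1.0 SD bias was 0.002 and −0.002 SD, and type I error 3.6% and 3.8%. Methods that the plan names would therefore remove selection on the baseline score. This stands, and it limits the point to what the plan permits. But the plan commits to neither model, gives no GEE working correlation in its analysis text, and also allows change scores and listwise deletion. With an independence working correlation the arm-by-time estimate would be the completer contrast of 0.10 SD minus a full-sample baseline contrast of zero, so the bias would remain.

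Other objections also stand. The plan does not use the word pooled; that reading rests on arm being mentioned only for the attrition rate. Opposite-direction loss is an assumption that nothing in the documents suggests, and one-arm selection is close to harmless. Hypotheses 1 and 2 are dichotomous, with non-response counted as failure in the power paragraph and clinic records added when available. If the score comparisons count as secondary, Bonferroni applies and .05 is not their threshold.

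A reader might infer that the 32% miss rate is the chance of a biased arm contrast. It is not: it concerns a difference common to both arms, which leaves the contrast unbiased at equal attrition. A reader might also infer that the plan cannot see arm-specific dropout at all, but it does compare rates by arm; what it does not compare is who leaves each arm. Nor do the documents support a claim that 3-month variables will be used as covariates; no passage proposes it.

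**Conclusion.** The concern holds in a limited form. Significance of a completer-versus-lost comparison, not split by arm, is a poor way to choose attrition covariates: it has limited power to show that a difference is absent, and it flags no more than about 5% of trials under the pattern that biases the contrast most. For completers-only analyses of continuous scores, the bias may then be about 0.10 SD with type I error about 8% at an assumed ±0.5 SD, rising to 0.20 SD and 19% at ±1.0 SD. If selection is in one arm only (0.5 SD), the figures are 0.04 SD and 5.6%. These results assume 20% loss in each arm, correlation .5, two-sided .05 and loss related to the baseline score.

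The documents do not support saying that biased contrasts will go unadjusted, only that they may. The dichotomous hypotheses are outside the point. It is a worthwhile, inexpensive improvement and not a failure of the main comparisons.

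**What to change.** In IV.F, for the continuous scores:

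- Drop significance as the trigger for adjustment, and drop the aim of ensuring that completers and those lost do not differ.
- For each score, always adjust for its baseline value plus a short fixed list already collected: for example clinic, pregnancy desire, motivation to prevent pregnancy and length of time in treatment. Alternatively, name one likelihood model that keeps all baseline values and includes these variables. Apply the choice whatever the completer-versus-lost comparison shows.
- Report completer-minus-lost differences separately by arm, standardised and with 95% confidence intervals, as description only. State that non-significance is not evidence that loss is ignorable.
- Add a delta-shift sensitivity analysis in which the values of the lost women are shifted in each arm separately, over a range fixed before follow-up data are examined, to show how large a departure would change the conclusion.

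The cost is a change of wording, a few degrees of freedom per model and a few hours of analysis, with no new data and no extra participants. The team also gives up a reassuring statement that no attrition bias was found when the intervals are wide. In return, RMSE falls from about 0.18 to 0.16 SD at correlation .5 even when dropout is harmless.

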**I. Hypotheses and Specific Aims:**

Developing effective reproductive health interventions for women in treatment for substance use disorders has tremendous potential to improve the health of women and children. In the US nearly half (51%) of all pregnancies are unplanned (L. B. Finer & Zolna, 2014). A recent study of pregnant women entering opioid medication-assisted treatment found much higher proportions – 86% described their current pregnancy as being unintended and about a third of these pregnancies were described as being unwanted (Heil et al., 2011). Women with unintended pregnancies had higher rates of recent substance use and almost all (90%) had a history of prior treatment for substance use disorders. Thus, substance use treatment programs are promising venues for addressing contraception.

Although there is a paucity of interventions specifically focused on preventing unintended pregnancies among women with substance use disorders, prior research from the addiction treatment and reproductive health fields provides relevant guidance for selecting key intervention elements. The addiction treatment field has an established history of using peers to support recovery (White, 2004). Peers have been used in effective HIV prevention interventions with vulnerable and hard to reach populations (Kelly, 2004; Kelly et al., 1991) and with adolescents (Brindis, Geierstanger, Wilcox, McCarter, & Hubbard, 2005; Key, Gebregziabher, Marsh, & O'Rourke, 2008). Involving individuals with similar life experiences may foster trust in intervention programs and increase sensitivity to the perspectives of the individuals in the target population. Thus, we propose to involve peers in a contraceptive and reproductive health education among women in treatment settings.

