- a. Conduct up to 30 individual qualitative interviews to better understand: pregnancy desires/motivation and perceived susceptibility and severity; and contraceptive knowledge, perceived benefits/barriers, self-efficacy, social norms, behaviors and access to contraception and family planning services, especially related to LARCs.
- b. Combine information from the qualitative interviews with HBM theory and results of prior research to specify the peer-led intervention.
- c. Assess acceptability and feasibility of the intervention in two focus groups and refine.
- d. Pilot the intervention with 10 women and finalize.

**Aim 2.** To assess acceptability, feasibility and the initial efficacy of the behavioral intervention ( $n=75$ ) as compared to usual care in substance use treatment ( $n=75$ ).

**Aim 3.** To conduct exploratory analyses to identify HBM constructs that are the most influential on LARC use

**Hypothesis 1.** Participants randomized to the intervention will be more likely to follow-up with a family planning clinic visit.

**Hypothesis 2.** Participants randomized to the intervention will be more likely to initiate Long Acting Reversible Contraceptive (LARCS) methods.

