***Theory to inform the study.*** Recent contraceptive interventions have not relied as heavily on theory as HIV prevention interventions. In a review of theory-based contraception interventions, the most heavily used theoretical basis was social cognitive theory (SCT) (Lopez, Tolley, Grimes, Chen, & Stockton, 2013). HBM is a social cognitive framework that applies a multidimensional approach to decision making and heavily relies on modifiable cognitive factors (Rosenstock, 1974). HBM will be used to guide the overall framework for operationalizing intervention content and measurement. HBM consists of 6 constructs that influence individual health related decision making and behaviors: perceived susceptibility (chance of getting a condition); perceived severity (seriousness of

the condition and its consequences); perceived benefits (ability of the preventive behavior to reduce risk); perceived barriers (the cost of the preventive behavior); cues to action (internal and external signals that trigger action) and self-efficacy (confidence in one's ability to take action). Self-efficacy, a component of HBM and an essential construct in Social Cognitive Theory (Bandura, 1986), has been utilized in many health studies and has been found to be an important predictor of safer sex behaviors (Brien, Thombs, Mahoney, & Wallnau, 1994; Goldman & Harlow, 1993; Longshore, Stein, & Chin, 2006; O'Leary, Goodhart, Jemmott, & Boccher-Lattimore, 1992; Sikkema et al., 1995; Wulfert & Wan, 1993). Thus, contraceptive self-efficacy will be a specific focus in the intervention. A recent conceptual review of primary research articles applying HBM to family planning, consolidated past work to specify a contraception specific HBM framework to be used to guide future research, measurement and practice (Hall, 2012).

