Many of the variables will be either summary index scores or latent variables that assess the psychological, behavioral and biological constructs of interest. For example knowledge will be a summary score representing the number of variables the participant correctly endorsed, while motivation will be a mean score across multiple variables representing the underlying latent construct. The variable related to use of LARCs will be a dichotomous variable representing current use or no current use of a LARC method (IUD or Implanon), as will attending a family planning visit during the study period.

Separate analyses will be conducted for each of the hypothesis to understand differential change over time. This includes looking at change scores as well as analysis of variance. The expectations for hypotheses 1 and 2 are that they will significantly increase in the intervention group. Differences will be assessed from baseline to follow-up period for each analysis.

Additional regression analyses will be conducted to identify significant predictors of differential change over time in birth control method and family planning visit. This analysis will determine if the intervention condition is a significant predictor of change. The regressions will account for any important statistically significant differences between groups at baseline. These differences may include variables pertaining to demographics, psychosocial factors, and behavioral variables. Generalized estimated equations (GEE) will be used to account for the within-subject correlation of repeated measures by individual patients. Group designations for the outcome analyses will adhere to the intention to treat threshold. All Statistical analyses will be performed using SAS (version 9.1 or later, SAS Institute Inc, Cary, NC) software.

*Engagement variables.* We will collect and analyze engagement with the PN and attendance to each session. These analyses will be used to assess intervention fidelity and to describe the amount of intervention each participant received to understand acceptability of the intervention as well as the relationship of intervention dose to study outcomes. These data will include, intervention activities covered and descriptive information such as the number of sessions attended, and the number of interactions with

the PN.

We will also record intervention sessions with the PN to determine the fidelity in which each session has been administered.

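### Holm's procedure would serve the exploratory and secondary tests better than plain Bonferroni at the same .05 bound, and the plan should say which significance rule governs Aim 3

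*Combined protocol and SAP*

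**What the plan says.** Section IV.F of the combined protocol and SAP gives two significance rules in consecutive sentences.

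- **Unadjusted rule.** It begins "The number of planned comparisons will be limited based on a priori hypotheses" and continues: "therefore the per comparison error rate of .05 will be used to evaluate significance of the specific aims".
- **Adjusted rule.** "Exploratory or secondary analyses will be adjusted for multiple comparisons using the Bonferroni test".

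The section does not list which analyses are secondary or exploratory, and it gives no number of tests for the Bonferroni divisor.

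Aim 3 stands in section I, under the heading "Hypotheses and Specific Aims", and reads: "To conduct exploratory analyses to identify HBM constructs that are the most influential on LARC use". Only Hypotheses 1 and 2 are stated as hypotheses (family planning visit and LARC initiation). In section IV.F, Hypothesis 1 also carries a bullet on knowledge, self-efficacy and perceived benefit among participants who had a visit. That bullet is not labelled primary or secondary.

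**The concern.** There are two separate matters.

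1. **Choice of procedure.** Single-step Bonferroni tests every comparison in a family of m at .05/m. Holm starts at that level and relaxes it after each rejection. Where several effects are real, Bonferroni can therefore miss some that Holm would declare at the same guaranteed error bound.

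2. **Which rule covers Aim 3.** Taken literally, Aim 3 is both a specific aim and an exploratory analysis, so both sentences reach it. A construct whose p-value lies between .05/m and .05 is significant under one rule and not under the other. Unless the plan settles this in advance, the choice could be made after the results are known. The three scores under Hypothesis 1 have a similar gap, since the plan does not say which rule applies to them.

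**Working it through.** **Inputs.** From the Study Statistical Power paragraph of section IV.F: 75 per group, 80% power, a 23-point difference and a 50% average success rate for dichotomous outcomes; 60 per group at follow-up, 0.55 SD and 80% power for continuous outcomes. Sidedness is not stated; two-sided is assumed. The number of tests m is not stated. Section II says "HBM consists of 6 constructs that influence individual health related decision making and behaviors", but no section says that Aim 3 makes six tests, so a range of m is shown.

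**The plan's own figures.** For dichotomous outcomes with variance taken at 50%:
- SE = √(2 × 0.5 × 0.5 / 75) = 0.0816
- power = Φ(0.23/0.0816 − 1.96) = 80.4%

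Using 38.5% v 61.5%, with the null variance pooled, gives 81.1%. The stated 80% is reproduced by a two-sided, unadjusted .05 test.

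For continuous outcomes, a simple two-sample comparison gives:
- expected z = 0.55 × √(60/2) = 3.012
- power at .05 = Φ(3.012 − 1.960) = 85.4%, against the stated 80%

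The plan's figure is conservative on this basis. It also mentions a repeated-measures structure, which is not specified fully enough to check. The illustration below needs only the 0.55 SD and the 60 per group.

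**Bonferroni v Holm, m = 3.** Bonferroni tests each comparison at .05/3 = .0167, so power is Φ(3.012 − 2.394) = 73.2%. Holm steps through .0167, .0250 and .0500. Simulation with 400,000 runs per row and correlation between tests of 0, 0.3 and 0.5 (ranges cover all three) gave:

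| Effects real | Power per true effect, Bonferroni | Power per true effect, Holm | Family-wise error, Bonferroni | Family-wise error, Holm |
|---|---|---|---|---|
| 0 of 3 | – | – | 4.5-4.9% | 4.5-4.9% |
| 1 of 3 | 73% | 73% | 3.1-3.3% | 4.1-4.5% |
| 2 of 3 | 73% | 76-77% | 1.7% | 3.7-4.0% |
| 3 of 3 | 73% | 80-82% | – | – |

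No run had a Bonferroni rejection that Holm did not also make.

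**Aim 3 under each rule.** With m independent null tests at .05, the chance of at least one false rejection is 1 − 0.95^m:

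| m | Family-wise error, unadjusted .05 | Bonferroni level (first Holm step) |
|---|---|---|
| 2 | 9.8% | .025 |
| 6 | 26.5% | .0083 |
| 10 | 40.1% | .005 |

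For m = 6, correlated tests lower the unadjusted figure to 24.1% (correlation 0.3) and 20.7% (0.5).

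**The case against.** **Bonferroni is not wrong.** It controls family-wise error, and preferring Holm is a matter of efficiency. This stands. A reader might infer that the plan contains an error here; it does not.

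**The gain may be small.** This also stands. With one real effect there is practically no gain. The gain reaches about 7 to 9 points per test only if all three effects are real. A reader might single out that case and conclude that the trial loses this much power on its three scores. The documents do not support that. They do not label the scores secondary, so Bonferroni may not apply to them at all. The bullet also concerns participants who had a visit, whose number is unknown, so a comparison of 60 v 60 is an illustration only.

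**Holm's realised error is higher.** True when some effects are real, as the first table shows, but it stays under .05.

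**Aim 3 already has a rule.** The unadjusted rule is justified by limited a priori hypotheses. Aim 3 has no hypothesis and calls itself exploratory, and the next sentence deals with exploratory analyses. So the adjusted reading is the more natural one, and it would be too strong to say that the plan commits Aim 3 to unadjusted testing. What remains is that the operative words are "the per comparison error rate of .05 will be used to evaluate significance of the specific aims", with no exception for Aim 3.

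**Conclusion.** The point holds as an improvement and a clarification, not as a flaw in the main analyses. The two dichotomous comparisons of Hypotheses 1 and 2 are unaffected.

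Holm dominates Bonferroni at the same .05 bound. The gain in average power per true effect runs from about 0 to 9 points in the three-test illustration, which assumes 0.55 SD, 60 per arm, two-sided tests and correlation from 0 to 0.5.

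The Aim 3 overlap is real on the text. The 9.8% to 40.1% family-wise error arises only under the less natural, unadjusted reading, with all constructs null, independent tests and an assumed two to ten tests. A reader might take the six-test figure as the trial's actual error rate. That does not follow, because the plan neither fixes six tests nor clearly adopts that reading.

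**What to change.** Make three changes to section IV.F:

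1. Replace the Bonferroni test with Holm's step-down procedure for exploratory and secondary analyses.
2. State that the unadjusted .05 level covers only the two dichotomous comparisons of Hypotheses 1 and 2: attending a family planning visit and initiating a LARC.
3. State that the HBM-construct tests of Aim 3 form one Holm family, and that the knowledge, self-efficacy and perceived-benefit scores under Hypothesis 1 form a separate, secondary Holm family outside the unadjusted rule. List the tests in each family, since neither procedure can be applied until m is known.

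The third statement has to name the scores explicitly. They sit under Hypothesis 1, and without it they would fall under both rules.

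The cost is a few sentences and no new data. The one downside is that simultaneous confidence intervals matching Holm are less simple than Bonferroni's; the plan does not promise any.

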Information from the individual interviews will be combined with evidence from the literature to further specify the intervention. The intervention will then be operationalized by creating a manual as well as a detailed outline that will be used to solicit feedback in the focus groups. We will then conduct two focus groups with the primary aim of obtaining women's feedback on the intervention and their thoughts on the most important aspects of HBM as related to contraception decision making and behavior. Focus groups are a strong addition to our formative methods, as they provide a cost-effective method of collecting information and a social forum to further evaluate the intervention. The social forum helps to identify salient issues and weed out extreme views that may have been obtained in the individual interviews (Agar & MacDonald, 1995). It also allows participants to interact and respond to each other's ideas. This synergy will provide valuable information in further refining the intervention. After each focus group, suggestions will be reviewed and needed modifications will be made to the intervention content and structure. Additionally, during this time, processes will be explored and put in place for referral to family planning services.

**B. Phase II.** We will then recruit 160 women in OMAT to participate in this phase of the study. Quantitative study data will be collected through participant surveys at baseline, 3 months, and 6 months follow-up. We will collect baseline data on a tablet, and 3 and 6 months follow-up using RedCap. A copy of this survey is included in this application and the content is as follows:

- Demographic data: Age, religion, sexuality, living situation, partnership status, previous pregnancies length of time in treatment and number of unique episodes
- Psychosocial: Knowledge of contraceptive methods and pregnancy risk; stage of change and level of motivation to prevent unintended pregnancies, attitudes towards different contraceptive methods, self-efficacy regarding condom and birth control use, ability to engage in preventive behaviors, partner communication, pregnancy desires
- Current behavior: In last 30 days and most recent: number of partners, number of vaginal sex acts, times used contraceptives, times used condoms, partner perceptions of contraceptives and condoms, risk behaviors.

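### Significance tests between randomised arms at baseline choose the covariates for the visit and contraception regressions, and baseline adjustment of continuous scores is not stated

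*Combined protocol and SAP*

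**What the plan says.** Section IV.F (Data Analysis Plan, Phase II) assigns multivariate regressions to Hypotheses 1 and 2. Before the primary analyses, "group differences in baseline measures will be evaluated to ensure that the group assignment was even".

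It then says: "Additional regression analyses will be conducted to identify significant predictors of differential change over time in birth control method and family planning visit". These regressions are also meant to show whether study arm predicts change. The covariate rule for them is: "The regressions will account for any important statistically significant differences between groups at baseline". The candidates are left open: "These differences may include variables pertaining to demographics, psychosocial factors, and behavioral variables". No covariate is named in advance, and the qualifier *important* is not defined.

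The Phase II data collection text (section IV.B) shows how wide the candidate set is. It includes "Demographic data: Age, religion, sexuality, living situation, partnership status, previous pregnancies length of time in treatment and number of unique episodes", psychosocial measures such as "stage of change and level of motivation to prevent unintended pregnancies, attitudes towards different contraceptive methods", and recent behaviour: "number of partners, number of vaginal sex acts, times used contraceptives, times used condoms, partner perceptions of contraceptives and condoms, risk behaviors".

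For change over time, section IV.F names change scores, analysis of variance and GEE for repeated measures. It does not say that the baseline value of a continuous score enters the model as a covariate. The power statement covers continuous outcomes compared by arm, and section IV.G promises evidence on the effect on knowledge. The baseline scores will be available: "Quantitative study data will be collected through participant surveys at baseline, 3 months, and 6 months follow-up".

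**The concern.** **Covariates for Hypotheses 1 and 2.** Under randomisation, a significant baseline difference between arms is a chance event. It is not evidence that the variable is related to a family planning visit or to contraceptive method. A strongly prognostic variable that happens to be balanced is left out, while an irrelevant one that happens to be imbalanced goes in. With an open candidate list and an undefined qualifier, the adjusted model is not fixed before the data are seen. Two analysts could properly report different estimates.

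**Continuous scores compared by arm.** If these are analysed as change scores, or by a GEE with baseline as one of the repeated responses, precision is given up although the baseline score needed to recover it is already collected. This part does not apply to LARC use, because current users are excluded at entry, or to a visit during the study period. It also leaves aside the statement under Hypothesis 1 on knowledge, self-efficacy and perceived benefit, which concerns women who attended a visit rather than randomised arms.

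**Working it through.** **Inputs from the documents (section IV.F unless noted).** Error rate .05 per comparison (two-sided assumed; sidedness is not stated); 75 per group, 23-point difference and average rate 50%, taken as 38.5% v 61.5%; 60 per group at follow-up, 0.55 SD, compound symmetry with correlation .5; baseline item list from section IV.B.

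**1. The plan's own figures.**
- Dichotomous: n = [1.96√(2 × .5 × .5) + 0.842√(.385 × .615 + .615 × .385)]² / .23² = 73 per group. At 75 per group, power is 81.1%. The stated 80% reproduces.
- Continuous: n = 2(1.96 + 0.842)² / .55² = 52 per group (53 by t test). At 60 per group, power is 84.8% by t test, and the difference detectable with 80% power is 0.516 SD. The stated 0.55 SD is conservative.

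**2. How often chance selects a covariate.** Counting each listed item once gives 8 demographic + 8 psychosocial + 6 behavioural = 22.
- Expected number selected: 22 × .05 = 1.1, whatever the correlation between items.
- Chance of at least one, independent items: 1 − .95²² = 0.676. For 10 items it is 0.401 and for 30 items 0.785.
- Chance of at least one of 22 equicorrelated items (200,000 draws; correlations assumed): 0.567 at 0.3 and 0.437 at 0.5.

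These figures read the rule as significance alone. A further filter for importance would lower them by an unknown amount.

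**3. Effect on the binary comparison.** Simulation of 20,000 trials: 75 per arm, logistic Wald test at .05, 22 standard normal items, each entered if its t test between arms has p < .05.

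| Setting | Arm only | Rule | Item named in advance |
|---|---|---|---|
| Power, independent items, none prognostic | 79.2% | 78.7% | – |
| Type I error, same setting | 4.6% | 5.0% | – |
| Power, items correlated 0.3, none prognostic | 79.2% | 78.9% | – |
| Type I error, same setting | 4.6% | 5.2% | – |
| Power, one item with latent correlation 0.3 with outcome (assumed) | 79.1% | 78.9% | 82.6% |
| Type I error, same setting | 4.7% | 5.0% | 5.3% |

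In the first setting (power row), at least one item is selected in 67.4% of trials and two or more in 29.9%. When something is selected, the median standard error rises 3%, and the odds ratio shifts by 5.4% at the median and 15.5% at the 90th percentile. Over all trials, the verdict at .05 differs from the arm-only model in 3.7%.

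**4. Continuous scores.** Variance factors in SD² units at correlation .5, with power and detectable difference from the noncentral t at 60 per group, two-sided .05:

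| Analysis | Variance factor | Power at 0.55 SD | Detectable at 80% |
|---|---|---|---|
| One follow-up, follow-up score alone | 1.00 | 84.8% | 0.516 SD |
| One follow-up, change score | 2(1 − .5) = 1.00 | 84.8% | 0.516 SD |
| One follow-up, baseline-adjusted | 1 − .5² = 0.75 | 93.2% | 0.447 SD |
| Mean of two follow-ups, change | .75 + 1 − 2(.5) = 0.75 | 93.2% | 0.447 SD |
| Mean of two follow-ups, baseline-adjusted | .75 − .25 = 0.50 | 98.8% | 0.365 SD |

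The variance of the mean of two follow-ups is (1 + .5)/2 = 0.75.

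Sensitivity to the correlation, one follow-up, normal approximation: the detectable difference is 0.605 SD (change) v 0.488 SD (adjusted) at 0.3, and 0.396 v 0.365 SD at 0.7.

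**5. Does naming GEE settle it?** No. In a complete simulated data set with an exchangeable arm-by-time GEE and baseline as a repeated response, the two interaction estimates were 0.3198 and 0.4336, identical to the differences in mean change.

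**The case against.** **The regressions are labelled additional**, and the preceding paragraph gives separate analyses for each hypothesis with no covariate rule. This does not remove the point. The same section assigns multivariate regressions to both hypotheses, and the additional ones are meant to test the effect of study arm.

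**The practical effect on the binary outcomes is small.** This stands. Power and type I error hardly change, and the 3.5-point gain from naming a covariate in advance (79.1% to 82.6%) rests on a correlation the documents do not give. This part is mainly about pre-specification.

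**The rule is not wholly without return.** With one prognostic continuous baseline variable (correlation .5, 60 per group, difference 0.511 SD), power is 79.4% unadjusted, 80.4% with the rule and 89.1% with the variable fixed in advance. The return is real but tiny.

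**The count of 22 is a reading of the list.** True; the survey might yield more or fewer variables, and correlated items lower the 68%. Hence the range above.

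**The plan never ties change scores explicitly to a continuous comparison by arm, and its stated power is met anyway.** Both are correct, and the GEE identity is exact only with complete data. This part is therefore an omission and a gain in efficiency. It is not an error in the sample size.

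**Conclusion.** The concern holds on both parts. For Hypotheses 1 and 2, chance imbalance and an undefined judgement decide the adjusted model. Some covariate enters in roughly 44% to 68% of trials with 22 items, depending on the assumed correlation, and gives almost no precision in return. The typical consequence is a modest shift in the odds ratio. A changed verdict is uncommon (3.7% of trials under the plan's design rates with independent, non-prognostic items).

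For continuous scores compared by arm, baseline adjustment is not stated. At the plan's own correlation and follow-up size it would reduce the detectable difference from 0.516 to 0.447 SD with one follow-up.

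No sample size changes. The results rest on two-sided testing, mechanical use of the significance rule and normally distributed items. The change is worth making because it costs almost nothing.

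**What to change.** - Delete the sentence in section IV.F that selects covariates by significant baseline differences. Present baseline comparisons descriptively; they may still serve as a check on allocation.
- Before outcome data are seen, fix the covariates for the Hypothesis 1 and 2 models: study arm, plus any prognostic variable named in advance. Clinic site is a reasonable choice but is optional.
- For each continuous score compared by arm, state that its baseline value is a covariate (ANCOVA, or a baseline-adjusted GEE on the 3- and 6-month values) in place of change scores.
- Leave the sentence on variables related to loss to follow-up as it is. Including such variables can support the missing-at-random assumption.

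The cost is wording in the analysis plan only. Clinic site is known for every participant, and the baseline scores are already in the baseline survey.
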